Sponsor	The sponsor is the party that commissions the organisation or performance of the research, for example a pharmaceutical company, academic hospital, scientific organisation or investigator. A party that provides funding for a study but does not commission it is not regarded as the sponsor, but referred to as a subsidising party.
SUSAR	Suspected Unexpected Serious Adverse Reaction
UAVG	Dutch Act on Implementation of the General Data Protection Regulation; in Dutch: Uitvoeringswet AVG
WMO	Medical Research Involving Human Subjects Act; in Dutch: Wet Medisch-wetenschappelijk Onderzoek met Mensen

SUMMARY

Rationale: Observational studies showed that higher levels of physical activity compared to lower levels are associated with a 38% reduction in risk of breast cancer-specific mortality [1]. However, the causality and underlying mechanisms have not been elucidated. Recent studies in rodents have shown that exercise can directly affect cancer outcomes. Exercise training (voluntary wheel running) in mice results in an increase in intratumoral Natural Killer (NK) and T-cells, which contributed to a 50-60% reduction in tumor growth [2]. Further analyses showed that exercise induced an increase in epinephrine which resulted in mobilization of NK-cells into the circulation which were then activated and redistributed to the tumor as a result of the production of IL-6 released by contracting muscles [2].

It is unclear whether a physical exercise program that has been proven feasible and effective for improving physical fitness, fatigue, quality of life and chemotherapy completion in patients with breast cancer receiving (neo)adjuvant chemotherapy [3-7] can yield similar results on tumor responses in patients. A randomized controlled trial (RCT) in patients with breast cancer receiving neoadjuvant chemotherapy is needed to formally assess whether physical exercise would improve antitumor responses and patient outcome. Such a study would provide an opportunity to directly assess the effects of exercise on the tumor *in situ*. However, the latter requires an additional tumor biopsy which might be a great barrier for patients to participate in such a study. Therefore, a pilot study is needed to determine the feasibility of conducting a sufficiently powered RCT examining the direct effect of exercise on the tumor.

Objective: To 1) ***study trial feasibility*** in terms of patient enrollment and the percentage of tumor biopsies that can be examined successfully, and 2) ***generate preliminary data*** on the potential effects of exercise on immune function assessed in the tumor and in blood.

Study design: Multicenter randomised controlled feasibility trial

Study population: 20 adult patients who are scheduled for neoadjuvant chemotherapy consisting of 4 cycles of 2 or 3-weekly adriamycin/cyclofosfamide (AC), followed by 12 weekly cycles of paclitaxel (T) weekly +/- trastuzumab, for early (stage I-III) breast cancer.

Intervention: 6-week (during 2 or 3 treatment cycles) moderate to high intensity aerobic and resistance exercise program supervised by a specifically educated physical therapist.

Main study parameters/endpoints: Trial feasibility and preliminary effects on immune function. Measurements will take place at baseline (prior to chemotherapy) and after 2 or 3 cycles (6 weeks).

Nature and extent of the burden and risks associated with participation, benefit and group relatedness: Prior to start of treatment, a diagnostic biopsy (part of routine care), a blood sample and a fitness test will be performed in all participants. At this time point the

blood sample collection and fitness test will be combined in one visit. After two (3-weekly) or three (2-weekly) cycles of AC chemotherapy an additional biopsy and blood sample will be taken and patients will perform a fitness test. The risks of the blood drawing and fitness test are negligible. The risk of clinically relevant complications of a breast tumor biopsy was around 0,2% in a multi-institutional study in 1994 [8]. Nowadays, the risk of complications is even lower, due to technological improvements that are implemented. The biopsies are necessary to study the effect of an exercise intervention on tumor and infiltrating immune cells. The safety of the exercise intervention has well been documented [9].

1. INTRODUCTION AND RATIONALE

Evidence from randomized controlled trials, including our own, shows that exercise during cancer treatment benefits physical fitness, fatigue and quality of life [4, 5]. Additionally, women with breast cancer who exercised during chemotherapy appeared to have fewer dose adjustments [3, 7]. However, the effect of exercise on tumor growth is largely unknown, which limits implementation in clinical practice [10].

Observational studies showed that higher levels of physical activity compared to lower levels are associated with a 38% reduction in risk of breast cancer-specific mortality [1]. However, the causality and underlying mechanisms have not been elucidated.

Recent studies in rodents have shown that exercise can directly affect cancer outcomes. Exercise training (voluntary wheel running) in mice results in an increase in intratumoral NK and T-cells, which contributed to a 50-60% reduction in tumor growth [2]. Further analyses showed that exercise induced an increase in epinephrine which resulted in mobilization of NK-cells into the circulation which were then activated and redistributed to the tumor as a result of the production of IL-6 released by contracting muscles [2]. Importantly, studies in healthy people showed that epinephrine also results in NK-cell mobilization into the circulation within minutes of initiating exercise [11]. Whether this mechanism of action (Figure 1) of exercise can also increase NK-cell infiltration into the human tumor is unknown.

[figure not shown]

Figure 1. Mechanism of action of how exercise may improve immune response and reduce tumor growth [2].

Currently, no sufficiently powered randomized controlled trial among patients has investigated whether a supervised aerobic and resistance exercise intervention during chemotherapy would benefit the tumor response [12]. A study among patients undergoing neoadjuvant chemotherapy provides the unique opportunity to assess the direct effects of exercise on the tumor.

Considering the non-invasive nature and relatively low costs of exercise, knowledge of its potential to boost immune function can – if effective - improve clinical practice.

In preparing for a future sufficiently powered randomized controlled trial, it is essential to 1) ***study trial feasibility*** in terms of patient enrollment and the percentage of tumor biopsies that can be examined successfully, and 2) ***generate preliminary data*** on the potential efficacy of exercise on immune function (immune cell infiltration into the tumor and immune cell functionality in blood).

Tumor tissue will be investigated by immunohistochemistry (IHC) to assess immune cell infiltration into the tumor with a specific focus on NK-cell frequency and phenotype. Tumor tissue will be obtained with tumor biopsies. ***Tumor biopsies*** at diagnosis are performed as part of usual care. An additional tumor biopsy will be performed after 2 or 3 cycles of chemotherapy (6 weeks). Other clinical trials among patients during neo-adjuvant treatment for breast cancer have also incorporated additional tumor biopsies (e.g., NCT03283384). A timeframe of 6 weeks was chosen to outweigh the presence of sufficient tumor tissue with sufficient physiological responses to exercise. Results from pre-surgical exercise interventions in patients with cancer indicate that physiological changes can already occur within 4 weeks of exercise training [13].

2. OBJECTIVES

Primary Objective: To study trial feasibility in terms of patient enrollment and the percentage of tumor biopsies that can be successfully assessed for changes in immune cell and NK cell content.

Secondary Objective(s): To study preliminary effects of exercise on immune cell function.

3. STUDY DESIGN

This is a multicenter randomized controlled feasibility trial, in which 20 women with breast cancer scheduled for neoadjuvant 2 or 3 weekly AC-T(H) chemotherapy will be randomized into a combined aerobic and resistance exercise intervention group or a usual care (no exercise)

control group, during the first 6 weeks (2 or 3 cycles) of chemotherapy. Patients from the control group will receive care as usual and are requested to maintain their usual daily physical activities. In order to limit contamination (increase of exercise in the control group), non-participation and prevent dropout, the control group will be offered the same 6-week exercise intervention after the tumor biopsy has been taken after 6 weeks. The study design and timepoints of measurements are presented in Figure 2.

[figure not shown]

Figure 2. Study design and time-point of measurements

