Patients from the control group will receive care as usual and are requested to maintain their usual daily physical activities. In order to limit contamination (increase of exercise in the control group), non-participation and prevent dropout, the control group will be offered the same 6-week exercise intervention after the tumor biopsy at T1 at the expense of the study-budget.

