6.3 Study procedures

After providing informed consent (IC), patients will be randomized in either the intervention or waitlist control group.

Participants in the intervention group will attend supervised exercise sessions twice a week at a local physical therapist and are encouraged to be physically active for at least 30 minutes per day at Borg level 12-14 (see paragraph 5.1).

Participants in the control group are requested to maintain their usual daily physical activities and are offered supervised exercise sessions after 6 weeks at the expense of the study budget (see paragraph 5.1).

Study parameters will be assessed at baseline (before start of chemotherapy) and after 6 weeks of chemotherapy (2 3-weekly or 3 2-weekly cycles) in the patient's own treating hospital. When patients are included from the Amstelland hospital they will be asked beforehand to come to the Amsterdam UMC – location VUmc for the physical test, blood samples and biopsy. Consequently, Amstelland will be a recruiting hospital in this study.

During the visits, information on physical fitness and blood samples will be collected. In addition, during the visit on T1 a tumor biopsy will be obtained. The T1 biopsy and physical fitness test will not be performed on the same day, as this might lead to contamination of the results on immunoreactivity in blood and tumor. We will strive to perform the physical fitness tests prior to the 3th (3-weekly) or 4th (2-weekly) chemotherapy administration so patients don't have to come to the hospital an extra time.

The visit on T0 will last approximately 75 minutes, the first visit on T1 (biopsy and blood sample) approximately 30 minutes and the second visit on T1 (physical fitness test) approximately 45 min.

Questionnaires will be sent to the participant's home and will take up to 10 minutes to complete, based on 6 items per minute. Questionnaires will be sent in paper only. Table 1 presents a summary of all study parameters.

	Measurement tool	-1	T0	T1
Primary outcome measurement				
Recruitment		X		
Quality of tumor material	Tumor biopsy		X	X
Secondary outcome measurement				
Clinical data				
Extent of the tumor	Medical records		X	
Disease, treatment and toxicity	Medical records		X	X
Performance status	Medical records		X	X
Co-morbidities and co-medication	Medical records		X	
Physical tests				
Aerobic fitness	Steep ramp test & endurance test		X	X
Muscle strength	1 RM legpress and 1 RM bench press		X	X
BMI	Height		X	
	Weight		X	X

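### The control arm is released to exercise at the T1 biopsy, although the T1 fitness test comes at a later visit with no maximum gap

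*Protocol*

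**What the plan says.** Three places in the protocol set the point at which controls may start the programme.

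- Section 3: "the control group will be offered the same 6-week exercise intervention after the tumor biopsy has been taken after 6 weeks".
- Section 5.1, usual care group: "the control group will be offered the same 6-week exercise intervention after the tumor biopsy at T1 at the expense of the study-budget".
- Section 6.3: controls "are offered supervised exercise sessions after 6 weeks at the expense of the study budget", with a reference back to section 5.1.

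None of them mentions the T1 fitness test or the T1 questionnaires.

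Section 6.3 then splits T1 into two visits: "The T1 biopsy and physical fitness test will not be performed on the same day". The reason given is to keep the fitness test from disturbing the immune readings in blood and tumour. The order follows from the visit durations: "the first visit on T1 (biopsy and blood sample) approximately 30 minutes", then "the second visit on T1 (physical fitness test) approximately 45 min". The only constraint on the date of the second visit is an aim: "We will strive to perform the physical fitness tests prior to the 3th (3-weekly) or 4th (2-weekly) chemotherapy administration". The questionnaires are posted to the patient's home. Table 1 assigns them to T1 but does not date them relative to the biopsy.

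**The concern.** Sections 3 and 5.1 delay the control programme partly to limit contamination. The chosen trigger protects the tumour sample but not the fitness measurement, which comes later.

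Section 6.1.2 gives fitness a specific task: to show whether six weeks of exercise produced the expected physiological response. That check helps in reading a null immune result. Control sessions before the test would narrow the difference between arms. Bench press is the clearest case, because section 5.1 lists it as a training exercise and section 6.1.2 uses it as a 1RM test.

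A lesser issue is the contamination questionnaire described in section 6.1.3. It asks controls about changed activity and structured exercise. If it is completed after the offer has been taken up, sessions that the study itself provided could be recorded as contamination. The T1 activity and quality-of-life questionnaires are open to the same overlap.

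**Working it through.** The point concerns the order of procedures. The protocol states no figure to reproduce, and no sample size, power or alpha value depends on it.

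**Step 1: order of events under the text**

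| Event | Where | Timing |
|---|---|---|
| T1 blood, then biopsy | 6.3 | First T1 visit |
| Programme offered to controls | 3, 5.1 | After the T1 biopsy |
| Programme offered to controls | 6.3 | After 6 weeks |
| T1 fitness test | 6.3 | Second T1 visit, another day |
| T1 questionnaires | 6.3, Table 1 | T1, posted, not dated against the biopsy |

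The offer can fall between the two T1 visits. Nothing in the available text asks controls to wait for the second.

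**Step 2: likely length of the gap**

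The protocol gives no gap, so it has to be assumed. The biopsy follows two three-weekly cycles (2 × 3 = 6 weeks) or three two-weekly cycles (3 × 2 = 6 weeks). The next administration is therefore due at about the same time. If the fitness test precedes it, as intended, the gap is a matter of days. I take 1 to 7 days as plausible. Fourteen days is shown only as an edge case.

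**Step 3: possible exposure**

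Inputs from section 5.1 are 2 supervised sessions per week and a 6-week programme, so 2 × 6 = 12 sessions. Sessions possible in a gap of g days = 2 × g / 7. Share of programme = sessions / 12.

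| Gap (assumed) | Sessions | Share of 12 |
|---|---|---|
| 1 day | 2 × 1/7 = 0.29 | 2.4% |
| 3 days | 2 × 3/7 = 0.86 | 7.1% |
| 7 days | 2 × 7/7 = 2.0 | 16.7% |
| 14 days | 2 × 14/7 = 4.0 | 33.3% |

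**Step 4: what this could do to the fitness difference**

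A share of sessions is not itself a change in endurance time or 1RM, and the protocol gives nothing to convert one into the other. As a rough bound, suppose that gains are proportional to sessions and that every control starts on the day of the biopsy. A 7-day gap would then leave 1 − 0.167 = 0.833 of the true difference, and a 3-day gap 1 − 0.071 = 0.929. If only one control in ten started early, the 7-day loss would be 0.1 × 16.7% = 1.7%. Proportionality and uptake are both assumptions.

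**Step 5: what is not exposed**

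The two feasibility criteria in section 6.1.1 are recruitment and successful biopsies at T0 and T1. Under sections 3 and 5.1 the T1 biopsy precedes the offer, and section 6.3 draws the T1 blood before the biopsy. Neither the feasibility criteria nor these immune outcomes can be altered by training that follows the offer.

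**Step 6: controls without a T1 biopsy**

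Section 6.3 excludes patients with low counts from the second biopsy, and section 6.5 mentions exclusion for infection. For such controls the trigger in sections 3 and 5.1 never occurs, and only the looser wording in section 6.3 applies.

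**The case against.** The strongest reply is that the biopsy marks the earliest point of an offer, not a start date. No text schedules a control session before the second T1 visit, and section 6.3 treats T1 as a single time point after six weeks. Arranging a local physical therapist also takes time. Training loads are set from the steep ramp test and 1RM, both repeated at T1, so testing first would be natural, although T0 values exist as well. Figure 2, which shows design and time points, is not reproduced in the text available here and may settle the order. Finally, fitness is a secondary outcome in a 20-patient pilot that calls itself underpowered for effects.

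Most of this stands, and it limits the size of the point. It does not remove it: the written trigger is the biopsy, and no available sentence closes the interval.

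A reader might infer more than the documents support:

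- **That controls will train before testing.** The overlap is permitted, not planned.
- **That a third of the programme could be delivered first.** This needs a 14-day gap, a full cycle on the two-weekly schedule, and so needs the stated aim to fail.
- **That the immune comparison is compromised.** The biopsy and blood are taken before the offer.
- **That squat training rehearses the leg test.** The tested lift is leg press, which is not among the exercises named in section 5.1. Only bench press appears in both lists.

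The questionnaire issue is weaker than the fitness issue, since Table 1 does assign the questionnaires to T1.

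**Conclusion.** The point holds as a minor wording defect. Sections 3 and 5.1 tie the control offer to a T1 procedure that section 6.3 places before the fitness test, and no maximum gap is set. The secondary fitness tests are exposed, and possibly the posted questionnaires. With an assumed gap of 1 to 7 days, exposure is probably 0 to 2 of 12 sessions per control who starts at once, and the resulting bias is small and toward no fitness difference. The conclusion rests on the text alone, since Figure 2 could not be consulted, and on the assumed gap.

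**What to change.** Reconcile sections 3, 5.1 and 6.3 so that all three state one trigger: the control offer starts after all T1 measurements are complete, meaning blood, biopsy where performed, fitness test and questionnaires. The phrase about the biopsy where performed also covers controls excluded from the T1 biopsy, for whom the present trigger in sections 3 and 5.1 never arrives. With this wording, the number of offered sessions possible before T1 measurement falls to zero.

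The cost is one phrase in each of three sections and a control programme that starts a few days later. Sample size and analysis do not change.

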4. STUDY POPULATION

4.1 Population (base)

Eligible patients will be recruited from Amsterdam UMC and 2 other sites.

4.2 Inclusion criteria

In order to be eligible to participate in this study, a subject must meet all of the following criteria:

- stage I-III breast cancer
- scheduled for neoadjuvant chemotherapy with 2 or 3-weekly Adriamycin/Cyclofosfamide, followed by Paclitaxel weekly +/- trastuzumab
- willing to undergo an additional ultrasound guided biopsy
- ECOG-performance score ≤ 2 (able to perform basic activities of daily living such as walking or biking)

4.3 Exclusion criteria

A patient who meets any of the following criteria will be excluded from participation in this study:

- addition of immuno- or targeted therapy at start of neoadjuvant chemotherapy
- currently participating in structured vigorous aerobic exercise and/or resistance exercise (≥ 2 days per week).
- cognitive disorder or severe emotional instability
- presence of other disabling co-morbidity that might hamper physical exercise e.g. heart failure (NYHA classes 3 and 4), chronic obstructive pulmonary disease (COPD, gold 3 and 4), orthopaedic conditions and neurological disorders (e.g., hernia, paresis, amputation, active rheumatoid arthritis);
- immunosuppressive medication (e.g. corticosteroids (other than used as part of standard chemotherapy premedication protocol), cyclosporine)
- immunodeficiency (primary or secondary)
- impossibility to perform an ultrasound-guided biopsy of the tumor

In case the treating physician experiences difficulties to determine whether a patient fulfils the physical exercise related criteria mentioned above, an experienced physiotherapist ([name]) will be requested for consultation.

4.4 Sample size calculation

Eligible patients will be recruited from Amsterdam UMC and 2 other sites. In these hospitals, over 100 patients receive neoadjuvant chemotherapy with Adriamycin/Cyclofosfamide treatment for breast cancer every year. With an anticipated accrual rate of 37% (corresponding to our previous REACT [14] and METRIC (NTR 4105) trials) recruitment will be completed after 7 months. In case accrual rates drop to 25%, patient enrollment will be completed after 10 months.

This study is a pilot trial focusing on evaluating study feasibility and preliminary effects of exercise on immune function. For the preliminary effects, the feasibility trial is underpowered by design. We will primarily explore the average size of the effect to identify whether it may have the potential to be clinically relevant, instead of observing statistical significance only ($p \leq 0.05$). Additionally, we will calculate the sample size required to detect the same difference in effect with 80% power (alpha 5%).

5. TREATMENT OF SUBJECTS

5.1 Investigational product/treatment

Exercise intervention

Patients in the exercise-group will follow a combined resistance and aerobic exercise program that was proven beneficial for physical fitness, fatigue, quality of life and chemotherapy completion rates in patients with breast cancer receiving adjuvant treatment [3]. This program meets the American College of Sports Medicine's exercise recommendations for patients with cancer¹¹. Exercise sessions take place 2 times per week for 60 min and include aerobic and resistance exercises at moderate-to-high intensity, in which the adequate training load will be tailored to a patient's individual fitness level throughout the intervention [3]. After a short warming-up (5 min), patients perform muscle strength exercises for 20 min per session, starting with two series of 12 repetitions at 70% of the one repetition maximum (1RM) per exercise and increasing gradually to two series of eight repetitions at 80% 1RM. The resistance program consists of at least six exercises targeting the large muscle groups with vertical row, squat, bench press, pull over, abdominal crunch and lunge. Aerobic exercises are performed for 30 minutes per session (with a minimal duration of ten minutes per exercise), with an intensity of 50% to 80% of the maximal workload (Wmax) as estimated by the Steep Ramp Test (SRT). The intensity of aerobic exercises is increased if a patients scores a 12 or lower on the Borg scale of perceived exertion, while the intensity is decreased at a score of 16 or higher. The heart rate should be

within a heart rate zone of 60% to 90% of the maximal heart rate, which is conventionally estimated as 220 minus age [3].

Exercise sessions are supervised by a specially educated physical therapist via the OncoNet network (www.onconet.nu) allowing patients to train close to their homes [3].

Additionally, patients are encouraged to be physically active for 30 minutes on at least 3 other days in the week at Borg level 12-14.

Patients in the exercise group are asked to keep an exercise log to register home-based physical activity.

Usual care group

Patients from the control group will receive care as usual and are requested to maintain their usual daily physical activities. In order to limit contamination (increase of exercise in the control group), non-participation and prevent dropout, the control group will be offered the same 6-week exercise intervention after the tumor biopsy at T1 at the expense of the study-budget.

